
## 5.4 Sample Size Calculation

Data for this pregnancy Registry will be regularly collected until the sample size required to detect a 2-fold or greater increase relative to the expected background rate of all birth defects and spontaneous abortions is reached. This will provide an adequate sample to ensure understanding of maternal drug safety. The Registry will be closed to new entries once this number of women with validated follow-up information has been reached and in agreement with the EMA; the data will be transferred to another independent Registry, if in acceptance with the other Registry, and according to ethical standards and national legislation at that point in time. These data will then be compared to background rates to see if there has been a significant increase in birth defects or pregnancy loss amongst these patients. A sensitivity analysis will be performed on the data to check other contributing factors.

The following sample size is derived to detect a clinically significant difference (i.e. a >2x increase in the outcome of concern) relative to expected background rates. In Europe, the assumed background risk of all reported birth defects is 23.719 per 1,000 births (EUROCAT, 2009) and the background rate of spontaneous abortion is 85.6 per 1,000 (Tata *et al*, 2005). Thus, assuming 80% power, 0.05 significance level (one-sided) and a loss to follow-up rate of 5%, we would require 376 pregnant women exposed to EurartesimTM in order to be able to detect a 2-fold or greater increase in birth defects and a 1.5-fold or greater incidence in spontaneous abortions with a one-group test. Calculations are based on a normal approximation to a Binomial distribution (equivalent to a chi-square test). Employing a 5% loss to follow-up rate is deemed appropriate as

utilising the services of ProClinica (refer to Section 7.3) to actively follow-up patients via direct patient contact should reduce the degree of loss to follow-up in this Registry.

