#### Primary analysis

In accordance with the primary objectives of the study and the way the study was powered, the main focus of the statistical analysis will be estimation of the incidences of birth defects and spontaneous abortion. 95% confidence intervals will be computed around these incidences in order to judge whether there is an increase of these incidences as compared to background risks.

In order to control for potential confounders, birth defects and spontaneous abortion will be described according to parameters such as concomitant infections/diseases and medication use. For spontaneous abortions, women who discontinued the study prior to delivery will not be taken into account in the primary analysis. A sensitivity analysis will be performed considering all patients, assuming that women who discontinued the study prior to delivery had experienced spontaneous abortion; this will provide us with the highest estimation of incidence of spontaneous abortion (i.e. the worst-case scenario).

In the same way, in the primary analysis, incidences of birth defects will be analysed without considering patients who discontinued the study prior to 14 weeks after the end of pregnancy. A sensitivity analysis will be performed on all patients assuming that women who discontinued the study prior to 14 weeks after the end of pregnancy had experienced birth defects.

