## 6.4 Lost to follow-up

Outcomes among pregnancies lost to follow-up could differ from those with reported outcomes. Patients will be considered lost to follow-up if a patient's expected delivery date has passed and outcome data have not been entered into the Registry within one year following the expected delivery date. Reasons of loss to follow-up will be documented. In order to investigate this further and determine the extent to which the results may be affected by loss to follow-up, a sensitivity analysis will be executed, in the same manner as described in the 'Primary analysis' part of Section 5.7.

In order to reduce the number of lost to follow-up patients, the option for each patient to be contacted by a specialized patient management unit (ProClinica, refer to Section 7.3) run by our CRO partner has been built into the Registry. Such contact will provide ongoing patient contact to remind the patient-participant of the importance of her ongoing participation in the Registry.

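### Counting every dropout as an event puts the birth-defect sensitivity analysis above background at the planned 5% loss whatever is observed, and imputes outcomes that the protocol's own definitions or visits rule out or contradict

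*Protocol*

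**What the plan says.** Section 5.7 (Primary analysis) judges an increase by setting a 95% confidence interval for each incidence against the background risk. Section 5.4 supplies the backgrounds: "the assumed background risk of all reported birth defects is 23.719 per 1,000 births", and "the background rate of spontaneous abortion is 85.6 per 1,000".

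For birth defects, the primary analysis leaves out women who discontinued before 14 weeks after the end of pregnancy. The sensitivity analysis brings all patients back, "assuming that women who discontinued the study prior to 14 weeks after the end of pregnancy had experienced birth defects".

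For spontaneous abortion, the primary analysis leaves out women who discontinued before delivery. The sensitivity analysis restores them, "assuming that women who discontinued the study prior to delivery had experienced spontaneous abortion; this will provide us with the highest estimation of incidence". The protocol calls this abortion version a worst case and introduces the defect version as parallel to it.

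Section 6.4 gives the purpose. To "determine the extent to which the results may be affected by loss to follow-up, a sensitivity analysis will be executed", in the manner of Section 5.7. The design in Section 5.4 rests on "assuming 80% power, 0.05 significance level (one-sided) and a loss to follow-up rate of 5" per cent, and concludes that "we would require 376 pregnant women exposed to Eurartesim".

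**The concern.** The planned loss (5%) is about twice the background defect rate (2.37%). If every lost woman counts as a defect, the imputed events alone can decide the comparison with background, and the observed infants no longer matter to the yes/no answer. Section 6.4 asks how sensitive the results are to loss, and an analysis whose answer is fixed in advance cannot say.

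The imputation also takes no account of what is already known about each woman. Some imputed outcomes are excluded by the protocol's own definitions, and others contradict examinations the protocol itself schedules.

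At stake is the reading of a safety registry required by the regulator. A null primary result would carry a sensitivity analysis showing an increase, and the reader could not tell whether it reflects the data or the imputation rule.

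**Working it through.** **Inputs.** From Section 5.4: N = 376; defect background p0 = 0.023719; abortion background 0.0856; planned loss 5%; targets 2-fold for defects and 1.5-fold for abortions. From Section 5.7: 95% interval against background. Exact limits are Clopper-Pearson; the lower limit for x events in n is the 2.5% quantile of Beta(x, n − x + 1).

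**The plan's own figure.** A one-group exact binomial test of 0.023719 against 0.047438, one-sided 0.05, first reaches 80% power at n = 357, and 357/0.95 = 375.8, so 376. (The normal approximation named in Section 5.4 gives 327.4, so 328, and 328/0.95 = 345.3, so 346. This does not affect the point.) The planned loss is 0.05 × 376 = 18.8, so 19 women, leaving 357.

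**Defects, none observed.** 19/376 = 5.05%, and 0.0505/0.023719 = 2.13 times background. The 95% intervals are:

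| Method | Lower | Upper |
|---|---|---|
| Exact | 3.07% | 7.78% |
| Wilson | 3.26% | 7.76% |
| Wald | 2.84% | 7.27% |

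Every lower limit is above 2.37%.

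**Defects at the background rate.** Expected 357 × 0.023719 = 8.47 cases; (8.47 + 19)/376 = 7.3%, or 3.1 times background.

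**Where the comparison flips (N = 376, exact).** 15 events give a lower limit of 2.25% and 16 give 2.45%, so the critical count is 16.
- With zero observed defects, 16 imputed losses (16/376 = 4.3%) suffice.
- With 8 observed defects, 8 losses (8/376 = 2.1%) suffice; with 9 observed, 7 suffice.
- With no drug effect, the probability of crossing is P(Bin(368, p0) ≥ 8) = 65% at 2% loss (8 women), P(Bin(365, p0) ≥ 5) = 93% at 3% (11 women), and over 99.9% at 4% (15 women).

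**Other denominators.**
- 376 followed out of 396 enrolled: 20/396 has a lower limit of 3.11%.
- A live-birth denominator of 70% to 90% of 376 (an assumption), with 5% of it lost and no defects: the exact lower limit is 2.66% to 2.96%. Only the Wald limit at 70% (2.32%) falls below background.
- Much smaller registries: 9/180 gives 2.31% and 5/100 gives 1.64%. Neither crosses.

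**Spontaneous abortion.** The 19 imputed events alone give 5.05%, below 8.56%, so the zero-event statement does not carry over. With no drug effect, 357 × 0.0856 = 30.6 events are expected, and (30.6 + 19)/376 = 13.2%, or 1.54 times background, just above the 1.5-fold target. The critical count is 44 of 376 (lower limit 8.63%; 43 gives 8.40%), so 25 observed events suffice: P(Bin(357, 0.0856) ≥ 25) = 88%.

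**Imputed outcomes against the protocol's own rules.**
- Sections 5.5 and 7.4.1 place spontaneous abortion at or before 28 weeks. The imputation covers any discontinuation before delivery, so a woman last seen pregnant at the visit 4 weeks before her due date is counted as an abortion.
- Section 5.5 lists birth defects at the end of pregnancy and at 6 weeks; the 14-week list has no such item. An infant recorded as normal at both assessments, then lost before 14 weeks, is counted as having a defect.

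**The case against.** The strongest reply is that an all-events bound is meant to be extreme. The protocol calls the abortion version a worst case and presents the defect version as its parallel, and a conservative bound is reasonable in a safety registry. That stands, and is why the figure should be kept. It does not meet the purpose in Section 6.4: when a bound crosses whatever is observed, its crossing carries no information.

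A second reply is that graded sensitivity analyses belong in the statistical analysis plan, which is not at hand. Their absence alone would be no finding. The point here is a rule that the protocol states, and which populations it imputes.

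Third, the 5% is borrowed. Sections 5.5 and 6.4 define loss as no outcome data within one year after the expected delivery date, whereas the imputation uses discontinuation before 14 weeks after the end of pregnancy, or before delivery. The protocol gives no rate for either. Actual figures could be lower, since active follow-up is planned, or higher.

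Fourth, a normal examination at 6 weeks does not exclude a defect found later, and Section 5.5.1 allows for paediatric confirmation afterwards. True, but that supports a small residual risk, not certainty.

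A reader might infer several stronger things that the documents do not support:
- That the analysis gives the same answer whatever the drug does. Only the yes/no comparison for defects is fixed, and only at about 4.3% loss or more with N near 376. The estimate still moves: 5.05% with no defects, 7.3% at background, and (16.9 + 19)/376 = 9.6% with a true doubling.
- That a doubling is demonstrated. With zero defects only the point estimate exceeds 4.74%; the lower limit of 3.07% does not.
- That nothing else addresses loss. Reasons for loss are documented, outcomes are actively screened, and Kaplan-Meier methods are planned for time-to-event variables.
- That a woman who left after an abortion is counted as a malformed live birth. Section 5.7 does not say how completed abortions enter the rule.

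**Conclusion.** The concern holds in a limited form. If the planned 5% loss applies to the imputation cut-offs and N is 376, the defect sensitivity analysis lies above background with zero observed defects (5.05%, exact lower limit 3.07% against 2.37%), so its comparison with background cannot tell a robust result from a fragile one. Crossing needs 16 losses (4.3%) with no defects, or about 8 (2%) with background-level defects; it need not occur at lower loss or in a much smaller registry. For abortions crossing is likely (88% with no drug effect), not certain. This takes the lower 95% limit above background as the criterion, which is the natural reading of Section 5.7, although no formal decision rule is set for the sensitivity analysis.

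Independently of the loss rate, the rule as worded imputes abortions outside the protocol's definition and defects that contradict recorded assessments. The primary estimates are not affected.

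**What to change.** Revise the rule in Section 5.7, to which Section 6.4 refers:

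- Impute spontaneous abortion only for women last known to be pregnant at or before the protocol's own abortion cut-off.
- Impute a birth defect only where no infant birth-defect assessment was recorded.
- Add a tipping-point table for each outcome. Set the event rate among the unknown to k times the observed or background rate (for example k = 1, 2, 3, 5), and report the number of events among the unknown at which the conclusion changes.
- Keep the all-events figure for both outcomes, labelled explicitly as an extreme upper bound.

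The cost is a wording change and one extra programmed table. The imputation needs only the last known gestational week and whether an infant assessment was recorded, which should follow from the visit dates, the last menstrual period or due date, and the assessments already planned.

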#### Description of the study populations

- HCPs:

HCPs will be described according to the data included in the HCP enrolment form. Tables and listings describing participating HCP characteristics will be produced (specialty, years in practice, geographic location, institution type, number of pregnant malaria (Registry) patients treated/site).

- Patients:

Patients included in the study will be described according to demographic and background characteristics (e.g. age, ethnicity, duration and timing of exposure to EurartesimT).

#### Pregnancy-related information

Frequency and type of pregnancy outcome will be stratified by the earliest trimester of exposure, demographics and medical background characteristics. Gestational weeks will be counted from the date of the last menstrual period, with the second trimester as beginning at week 14 and the third trimester as beginning at week 28. Women who discontinued the study prior to delivery will not be taken into account in the primary analysis. A sensitivity analysis of patients who did not complete the entire follow-up will be performed for the main study outcomes, in the same manner as described above in the 'Primary analysis' section.

Time-to-event variables will be analysed via survival analysis methods (e.g. Kaplan-Meier survival estimates and associated confidence intervals).

In order to control for potential confounders, pregnancy outcomes will be analysed according to parameters such as lifestyle factors, concomitant infections/diseases and medication use. Patient's Body Mass Index (BMI) will be calculated from the patient's height (cm) and weight (kg) data, using the following equation:

#### $BMI = \underline{Weight (kg)}$

Height (meters)

The BMI outcome value will be categorised as follows:

- BMI <18.5 = Underweight
- BMI 18.5-25 = Healthy weight
- BMI >25 = Overweight

In order to optimize patient recruitment, patients with recurring malaria and Eurartesim™ use during pregnancy will be included in this pregnancy Registry in addition to first malaria infections. However, first and recurring malaria infections will be analyzed separately due to the potential differences in disease aetiology and pregnancy outcomes.

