#### 26/06/2012 Version - 12.0

#### **TABLE 1: STUDY FLOW CHART**

Assessment by HCPs	Visit 1 (Enrolment)	Visit 2 (4 weeks post- enrolment)	Visit 3 (4 weeks prior to expected due date)	Visit 4 (end of pregnancy)	Visit 5 (6 weeks after end of pregnancy)	Visit 6 (14 weeks after end of pregnancy)	Visit 7 (12 months after end of pregnancy)
Date of the visit	x	x	x	x	x	x	x
Socio-demographic characteristics	x *						
Lifestyle data	x						
Malaria history	x						
Date of exposure to Eurartesim ™	x						
Pregnancy data and obstetrical history	x						
Maternal complications	x	x	x	x	x	x	
Fetal complications	x	x	x	x			
Concomitant medication use	x *	x	x	x			
Significant medical history	x*						
Exacerbation of pre-existent clinical condition		x	x	x			
Comorbidities		x	x	x			
AEs/SAEs		x	x	x	x	x	X
Maternal mortality				x	x	x	
Infant mortality				x	x	x	
Infant development					x	x	X

\*These data will also be collected for the biological father.

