#### At enrolment visit:

- Date of the visit.
- Socio-demographic characteristics of the mother (ethnicity [based on the standard definitions of ethnicity used in the EU country where the woman is enrolled in the Registry], country of birth, primary language and socio-economic status [based on current or most recent occupation and years of formal education]).
- Socio-demographic characteristics of the biological father (age and current or most recent occupation).
- Mother's lifestyle data (height [cm] and weight [kg], radiation exposure, smoking status [never/past/current], alcohol consumption [weekly units], recreational drug use.
- Mother's malaria history (date of malaria diagnosis, date of most recent Eurartesim™ administration and dose, previous Eurartesim™ administrations, other treatment taken for malaria).
- Pregnancy data (date the pregnancy was registered).
- Estimated date of delivery/date of last menstrual period.
- Previous or concurrent maternal complications.
- Health status of the fetus, if it is already known at time of enrolment, i.e. via ultrasound.
- Pregnancy outcome, if already known at time of enrolment.

- Obstetrical history (number of previous pregnancies and outcome).
- Significant medical history of the mother and the biological father.
- Concomitant medication use in the mother and the biological father in the one (1) month (30 days) prior to conception.

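### BMI is calculated from a weight taken at enrolment, at any gestation, and cut at fixed limits of 18.5 and 25, so the BMI category would partly reflect how far the pregnancy had advanced

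*Protocol*

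**What the plan says.** The enrolment list in Section 5.5 (repeated in the Section 2 summary) asks for "Mother's lifestyle data (height [cm] and weight [kg], radiation exposure" and other lifestyle items. Table 1 schedules "Lifestyle data" at Visit 1 only. No other maternal weight is scheduled, and no pre-pregnancy or booking weight is requested.

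Under Pregnancy-related information, Section 5.7 says that BMI "will be calculated from the patient's height (cm) and weight (kg) data, using the following equation", namely weight in kilograms over height in metres squared. The classes are "BMI <18.5 = Underweight", "BMI 18.5-25 = Healthy weight" and "BMI >25 = Overweight". No reference time for the weight is given and gestation is not mentioned.

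Section 5.2 admits women exposed from 30 days before conception to any time after it. The enrolment list allows for a pregnancy outcome that is already known. BMI is introduced in the Section 5.7 paragraph that analyses pregnancy outcomes by lifestyle factors, among others, as a means of controlling confounding. The one caveat on BMI, in Section 6.2, concerns under-reporting by patients.

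**The concern.** Weight rises during pregnancy, and the limits of 18.5 and 25 are applied as if it did not. With a weight from the visit, a woman in the upper part of the healthy class can be classed healthy if she enrols early and overweight if she enrols late. By the same mechanism, some underweight women who enrol late move into the healthy class.

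The secondary outcomes in Section 7.4.1 include spontaneous abortion and low birth weight. A woman enrolled late and prospectively can no longer have an early loss, and she is also more likely to be labelled overweight. An association between BMI class and loss could therefore arise from entry time alone, while true maternal BMI stays incompletely controlled. Under-detection of underweight would weaken any description of birth weight by BMI.

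An SAP cannot repair this fully. If the CRF never captures a pre-pregnancy weight, or never marks which weight was recorded, that information cannot be recovered at analysis.

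**Working it through.** The plan gives no figure on this point to reproduce. The check has two parts: whether the text leads to the problem, and how large the problem could be.

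**Inputs from the protocol**
- Height and weight are collected at Visit 1 only (Table 1; Section 5.5).
- BMI = weight / height², with limits at 18.5 and 25 (Section 5.7).
- Enrolment is possible at any gestation or with the outcome known (Sections 5.2 and 5.5).
- In the cited study of 50 treated pregnant women (Section 3), gestation at treatment was 23.7 ± 8.2 weeks, range 9.2 to 39.1. This describes treatment in another population, not enrolment here. It shows only that a wide spread of gestation is plausible.

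**Assumptions, not in the documents**
- Height 1.65 m.
- Pre-pregnancy BMI normal, mean 23 to 25, SD 4 to 5; central case mean 24, SD 4.5.
- Weight gain at enrolment of 1, 2, 5, 10 or 12.5 kg.

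**Step 1: shift in BMI.** Shift = gain / 1.65² = gain / 2.7225.

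| Gain (kg) | Shift | Pre-pregnancy BMI above which a woman is labelled overweight (25 − shift) |
|---|---|---|
| 1 | 0.37 | 24.63 |
| 2 | 0.73 | 24.27 |
| 5 | 1.84 | 23.16 |
| 10 | 3.67 | 21.33 |
| 12.5 | 4.59 | 20.41 |

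Example: a woman of 62 kg has BMI 62 / 2.7225 = 22.8. At 72 kg it is 26.4.

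**Step 2: share of the healthy class relabelled overweight.** Share = P(25 − shift < BMI ≤ 25) / P(18.5 ≤ BMI ≤ 25).

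Central case, Normal(24, 4.5): P(BMI ≤ 25) = 0.588 and P(BMI < 18.5) = 0.111, so the denominator is 0.477.
- 5 kg: (0.588 − 0.426) / 0.477 = 34%.
- 10 kg: (0.588 − 0.276) / 0.477 = 65%.
- 12.5 kg: (0.588 − 0.212) / 0.477 = 79%.

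Over all combinations of mean 23 to 25 and SD 4 to 5:

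| Gain (kg) | Lowest (mean 23, SD 5) | Highest (mean 25, SD 4) |
|---|---|---|
| 1 | 6% | 8% |
| 2 | 12% | 16% |
| 5 | 30% | 40% |
| 10 | 61% | 72% |
| 12.5 | 75% | 84% |

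Wider assumptions (height 1.63 m, mean 22 to 26, SD 3 to 5) give 4-25% at 1 to 2 kg, 27-55% at 5 kg and 71-93% at 12 kg.

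**Step 3: what cannot be computed.** These shares hold at a given gain. A registry-wide share would need the distribution of gestation at enrolment, which the protocol does not give.

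**The case against.** **The weight is not labelled.** The protocol never says that it is the current weight. The same enrolment list asks for items that look back, such as past smoking and medication in the 30 days before conception. Section 6.2 names BMI among the items patients may under-report, which suggests self-report. Section 7.4 says that the CRF is still to be developed. A pre-pregnancy weight is therefore not excluded. This stands: the misclassification is conditional on the reading. It does not remove the point. Where the list wants a pre-conception reference it says so, and it does not for weight. If sites read the field differently, the data would mix two kinds of weight without a marker.

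**The primary result is untouched.** This also stands. The primary analysis estimates incidences with 95% confidence intervals against background rates. The parameters it names are concomitant infections or diseases and medication use. No BMI-adjusted model is specified. With 376 × 0.95 ≈ 357 women followed, the background rate gives 357 × 0.023719 ≈ 8.5 birth defects, so three BMI strata could only be descriptive for that outcome.

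**A reader might infer that BMI becomes a proxy for exposure timing.** The documents do not support that. BMI would track gestation at enrolment, which can be well after exposure, and it would still carry true BMI. Earliest trimester of exposure is a separate stratifier. Because enrolment can follow exposure by months, that stratifier does not remove the effect of enrolment time either.

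**Gestation at enrolment can be derived** from the visit date and the last menstrual period or due date, so an SAP could analyse within it. That would limit the damage but would not restore a pre-pregnancy BMI.

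**Conclusion.** The point holds as a defect in how BMI is defined. Fixed limits are applied to a weight collected only at enrolment, in women who may enrol at any gestation or afterwards, with no reference time and no allowance for gain. If the weight is the one at the visit, the direction of error follows from the formula for any woman who has gained weight. On the stated assumptions the error is small early (about 6-16% of healthy-class women relabelled at 1 to 2 kg) and large late (30-40%, 61-72% and 75-84% at 5, 10 and 12.5 kg).

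The percentages rest on assumed height, BMI distribution and gain, and the number of women who will enrol late is unknown. The reach is the secondary analyses of pregnancy outcomes by lifestyle factors. The primary incidence estimates and the sample size are unaffected. It is worth correcting before data collection, because the missing weight cannot be supplied reliably later.

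**What to change.** In the enrolment lists of Sections 2 and 5.5, ask for pre-pregnancy weight, either self-reported or the first antenatal-booking weight from the record, with its date and source. In Section 5.7, state that the BMI classes are computed from that weight.

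Where only a later weight exists, record gestation at weighing, do not apply the 18.5 and 25 limits, and report or analyse that weight separately by gestation. Simply setting such women to missing would make missingness depend on gestation at enrolment, which is the same dependence the change is meant to remove. Keeping the later weight with its gestation retains the information.

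The cost is one CRF field with its date and a sentence or two of text. The downsides are some recall error in self-reported weight and some women left without a BMI class.
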